8.4 Reporting of Safety Events and Device Deficiencies/Complaints

The following events are to be reported to the Sponsor within 72 hours of the event occurrence and to the EC per their policy:

- All SAEs and USADEs
- All device issues that could possible lead to an SAE

Additional follow-up information may be requested by the Sponsor. In addition, safety information may be shared with regulatory agencies and other participating sites, as required by applicable law and regulation.

8.5 Device Deficiencies

Device deficiencies should be reported to the study Sponsor contact identified on the cover page of this protocol. All device deficiencies will to be collected, fully investigated, and documented in the source document and appropriate Sponsor document during the study reporting period. The PI is responsible for notifying the Sponsor in the event that there is any device issue that could potentially lead to a SAE.

9. ETHICAL CONDUCT OF THE STUDY

The study will be carried out in accordance with the protocol and with principles enunciated in the current version of the Declaration of Helsinki; the guidelines of Good Clinical Practice (GCP) for medical devices, as set forth by ISO 14155:2011 and ISO 14971:2012; applicable requirements of Health Canada's Medical Device Regulations (SOR/98-282); and other applicable regulatory authority requirements of Canada, as necessary.

The study will be conducted and reported in accordance with applicable policies of the local Ethics Committee (EC) and governing regulatory authorities.

If national or regional EC requirements are less strict than the requirements of GCP, such as ISO 14155:2011 for medical devices, the Sponsor shall apply the requirements of this International Standard to the greatest extent possible, irrespective of any lesser requirements, and shall record such efforts.

9.1 Ethics Committee

The responsible site PI will ensure that approval from an appropriately constituted EC is attained for the clinical study prior to enrolling subjects. The PI will also ensure that documentation of approval is maintained for the duration of the study.

The PI will ensure that the Sponsor is notified of any withdrawal of EC approval within 5 working days of such occurrence. If approval is terminated or suspended, the PI will promptly notify the Sponsor and provide written explanation.

9.2 Regulatory Agencies and Competent Authority

The Sponsor will obtain approval from the local regulatory agency or competent authority (CA), Health Canada, before the start of the clinical trial, if necessary, per applicable local laws and regulations. Any additional requirements imposed by the EC or CA shall be followed, when applicable.

9.3 Management of Protocol Modifications and Amendments

Substantial amendments will only be implemented after EC approval.

A deviation is any instance(s) of failure to follow, intentionally or unintentionally, the requirements of the protocol. Under emergency circumstances, deviations from the protocol to protect the rights, safety, and wellbeing of human subjects may proceed without prior approval of the Sponsor and the EC/CA. Such deviations shall be documented and reported to the Sponsor and the EC as soon as possible. Deviations will be reported as:

- **Critical Deviations:** Deviations that significantly affect the safety, efficacy, integrity, or conduct of the study. These deviations must be reported to the Sponsor no later than 5 working days from awareness of occurrence and reported to the EC per the deviation reporting policy.
- **Non-Critical Deviations:** Protocol deviations that do not significantly affect the safety, efficacy, integrity, or conduct of the trial. These deviations must be documented on the CRF Protocol Deviation page and will be reviewed by the study monitor.

Non-substantial modifications may be made during the normal course of device optimization, maintenance, and feasibility testing. Non-substantial modifications will be communicated to the CA as soon as possible, if applicable, and to the EC per their policy.

9.4 Participant Information and Informed Consent

The investigator will explain to each participant the nature of the study, its purpose, the procedures involved, the expected duration of exposure to the investigational device, the potential risks and benefits, and any potential discomforts. Each participant will be informed that participation in the study is voluntary, that he/she may withdraw from the study at any time, and that withdrawal of consent will not affect his/her subsequent medical assistance and treatment. The participant must be informed that his/her medical records may be examined by authorized individuals other than their treating physician.

All participants for the study will be provided with an ICF, describing the study and providing sufficient information to allow the participant to make an informed decision about his/her participation in the study. Informed consent documents will be subject to approval by the EC prior to enrolling subjects in the study.

The participant should read and consider the statement before signing and dating the ICF, and shall be given a copy of the signed document. The ICF must also be signed and dated by the investigator (or his/her designee), and it shall be retained as part of the study records.

9.5 Early Termination of the Study

The Sponsor may terminate the study prematurely according to certain circumstances. Examples of such circumstances include ethical concerns, insufficient participant recruitment, participant safety concerns, alterations in accepted clinical practice that make the continuation of a clinical trial unwise, early evidence of benefit or harm of the research product, or for any other reason.

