1.3 Controls and Minimization of Bias

All reasonable attempts will be made to control and minimize bias during this study, including the following:

- Subjects will be consecutively enrolled from the patients screened until the accrual quota is filled, with the intent of limiting selection bias;
- Spectrum bias will be limited by using a population expected to be representative of the general population at the investigational site, without regard to race or ethnicity.

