2.5 Anticipated Risks and Benefits

The device under study has undergone risk assessment, in accordance with International Standards Organization (ISO) 14971:2012, and risks have been mitigated to levels as low as reasonably practicable (ALARP).

The investigational OEC Elite is expected to present similar potential risks to patients, operators, or others in this study as the predicate commercial device, OEC 9900 Elite, when used under similar clinical indications for use. The risks of study participation are not expected to be different than those of non-study procedures. Because basic image guided fluoroscopy will be used for conventional procedure applications, there will be no post-trial care or follow-up required by this study.

As with all x-ray devices, OEC Elite uses the minimum possible ionizing x-ray radiation dose, which is within acceptable limits set forth by applicable local laws and regulations necessary to complete a procedure. Because the radiation dose and procedural duration widely vary for the procedures included in this study, there is no prospective per-procedure maximum radiation dose or duration prescribed by this protocol. All procedures will be conducted per the clinical standards of the site and the medical discretion of physicians performing the clinically indicated study procedures.

In the unlikely event that a device error prevents or impairs image acquisition, it is possible that a subject may require alternative or additional imaging to complete an intervention or exam. If imaging is not adequate or diagnostic-quality images cannot be obtained using the investigational device, the subject will not undergo additional investigational imaging. Necessary medical care will be provided by the sites, and equivalent, site-provided commercial fluoroscopy systems (e.g. the predicate device or equivalent) will be readily available throughout the study.

Subjects who undergo additional or elongated imaging procedures may be at a small increased risk because of additional x-ray exposure and possible additional procedure time, which may also impact the duration and/or dosages of anesthesia and contrast administration.

Subjects are not expected to benefit directly from study participation; however, the results may benefit future patients by helping to better understand the device under study.

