4.3 Number Subjects/Cases

Up to 40 subjects may be enrolled the site. Enrollment may be discontinued at any time prior to reaching 40 subjects at the discretion of the sponsor.

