10.3.1 Interim Analysis

No interim analyses are intended to be conducted as part of this study.

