11.1.1 Completion of Case Report Forms (CRFs)

The data reported on the CRFs shall be derived from source documents and be consistent with these source documents. Paper CRFs will be used to collect data. The Sponsor will provide CRFs and train study staff on completion of CRFs using Good Documentation Practices (GDP). CRF Completion Guidelines (CCG) may be provided by the Sponsor to help facilitate training.

CRFs are to be completed as information becomes available at the site. CRFs should be signed by indicated parties, in indicated area(s), to certify the contents of the form. The PI is ultimately responsible for ensuring completion of CRFs.

If discrepancies are discovered on paper CRFs during monitoring, the Sponsor's representative will ensure that the study staff makes necessary corrections directly to the CRF(s) prior to collection.

Following CRF collection, the Sponsor will review the data. A Data Clarification Form (DCF) may be provided to the site to correct or clarify discrepancies.

If a site discovers discrepancies after CRF collection, the site may notify the Sponsor and request data modification.

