12. MONITORING PLAN

In collaboration with the site, the Sponsor will ensure proper monitoring of the study to confirm that all the research requirements are met. Monitoring visits will oversee the progress of a clinical investigation and ensure that it is conducted, recorded, and reported in accordance with the protocol, written procedures, GCP ISO 14155:2011, and the applicable regulatory requirements.

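### Does the sponsor's freedom to stop early on evidence of benefit, with no interim analysis planned, bias the guidance-adequacy result?

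*Combined protocol and SAP*

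**What the plan says.** Section 9.5 reserves the sponsor's right to end the study and gives examples of circumstances: ethics, recruitment, safety, changed clinical practice, and "early evidence of benefit or harm of the research product, or for any other reason". Section 4.3 sets a ceiling and no floor: "Enrollment may be discontinued at any time prior to reaching 40 subjects at the discretion of the sponsor". Section 10.3.1 states: "No interim analyses are intended to be conducted as part of this study".

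Section 1.3 offers consecutive enrolment as a protection against selection bias: "Subjects will be consecutively enrolled from the patients screened until the accrual quota is filled".

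The primary endpoint (3.2.1) is the investigator's yes/no report, for each subject, of whether image guidance was adequate to complete the procedure. It is recorded on the case report form (7.3). The study is open label at one site (4.1). Section 11.1.1 has the sponsor's representative resolve discrepancies on paper forms at monitoring, and then says: "Following CRF collection, the Sponsor will review the data".

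Section 10.1 tests no hypothesis and 10.3 plans no analysis. Section 10.2 rests the sample size on past experience and on an expectation that the procedures will demonstrate clinical performance. It gives no rate, precision or target.

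**The concern.** A stop for early benefit presupposes that someone has looked at results, yet no look is planned. The protocol does not define benefit. Section 2.5 says "Subjects are not expected to benefit directly from study participation", so the only favourable results that could build up during enrolment seem to be the adequacy answers and the user survey. That reading is an inference; the text does not say it.

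The sponsor can see those answers as they arrive. The study is open label, the forms carry the endpoint, and nothing holds back sponsor review until enrolment closes. A sponsor could therefore stop after a good run. Good runs would then be frozen at a small number of subjects while poor runs continued towards 40, so the reported proportion would on average exceed the true one. Section 10.5 asks the final report to explain departures from the statistical plan, and a stop that 4.3 permits is not a departure. A reader might not learn whether logistics or a favourable count closed enrolment.

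**Working it through.** **Inputs.** From the documents: maximum 40 subjects, no minimum (4.3); a yes/no endpoint per subject (3.2.1). The documents give no adequacy rate, look time or stopping rule. True adequacy p of 85, 90 and 95% and the rules below are assumptions. The figure of 40 has no stated inputs, so there is no calculation of the plan's own to reproduce.

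**Step 1: the plan as written.** With 40 subjects, or with a stop unrelated to results, the expected proportion equals p and the bias is 0.

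**Step 2: one informal look.** Suppose the sponsor looks at subject k, stops if all k are adequate, and otherwise continues to 40. All k are adequate with probability p^k. On those paths the reported proportion is 1, where continuing would have given (k + (40 − k)p)/40 on average. Hence

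bias = p^k × [1 − (k + (40 − k)p)/40] = p^k × (40 − k)(1 − p)/40.

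For k = 10 and p = 0.90: 0.90^10 = 0.349; (30 × 0.10)/40 = 0.075; the product is 0.026, or 2.6 points.

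| Look at | Bias in points, p = 85 / 90 / 95% | Standard error √(p(1 − p)/k) in points |
|---|---|---|
| 5 | 5.8 / 5.2 / 3.4 | 16.0 / 13.4 / 9.7 |
| 10 | 2.2 / 2.6 / 2.2 | 11.3 / 9.5 / 6.9 |
| 20 | 0.3 / 0.6 / 0.9 | 8.0 / 6.7 / 4.9 |
| 30 | 0.03 / 0.1 / 0.3 | 6.5 / 5.5 / 4.0 |

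The standard error with all 40 subjects is 5.6 / 4.7 / 3.4 points. Biases from a look at 10 or later lie below that too; a look at 5 gives a bias of about that size. At k = 10 the rule would stop the study with probability 20 / 35 / 60%.

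**Step 3: the extreme.** A sponsor who knew p, looked after every subject and always stopped at the best moment could raise the expected proportion by 3.8 / 3.2 / 2.3 points if looks began at 10 subjects, and by 12.6 / 8.8 / 4.6 if they began at the first. The second case usually ends the study after one adequate procedure, with probability p, that is 85 / 90 / 95%. It is a mathematical limit, since no reader told that n = 1 would rely on the proportion.

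**Step 4: intervals.** Under the favourable-stopping rules tested (one look at 10 or 20; looks at 10, 20 and 30; looks after every subject from 10; p from 80 to 98%), ordinary exact 95% intervals covered the true rate at least 96% of the time. For the single look at 10 or 20 with p of 85 to 95%, coverage was above 98%. An exact interval reported without adjustment would not mislead.

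**Step 5: precision.** If all n subjects are adequate, the lower exact 95% limit is 0.025^(1/n): 69.2% at 10/10, 83.2% at 20/20, 88.4% at 30/30 and 91.2% at 40/40. Stopping at 10 instead of 40 lowers that limit by 91.2 − 69.2 = 22.0 points, far more than the 2 to 3 points of bias. The final n makes this loss visible.

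**Step 6: would barring favourable stops help?** Stops for poor imaging would have to stay open, and they bias the other way. Stopping at 10 subjects when 3 or more are inadequate gives −2.5 / −1.2 / −0.2 points. A one-sided pledge would leave that in place, and nobody could verify the sponsor's motive.

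**The case for a change.** The strongest case for acting is that the texts do pull against each other. Section 9.5 names a ground that can be used only after looking at results, 4.3 has no floor, and the sponsor has the forms in hand. Section 10.2 speaks of demonstrating clinical performance, so the adequacy count may be used as evidence even without a test, and a count used that way should not help determine its own sample size. The remedy would also be cheap: a sentence barring favourable stops and a line in the report.

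The tension in wording stands, as does the direction of the bias if the freedom were used that way. The rest is weaker. Section 9.5 is a general list of examples and does not mention adequacy; since 2.5 expects no direct benefit to subjects, the benefit ground can equally be read as having no application here. The access described in 11.1.1 is data cleaning: the representative "will ensure that the study staff makes necessary corrections directly to the CRF(s) prior to collection", and later queries go back to the site. Section 12 is similarly routine: "Monitoring visits will oversee the progress of a clinical investigation". Neither describes a running tally of outcomes. Consecutive enrolment under 1.3 limits selection among screened patients up to whatever point enrolment ends, so an early stop does not undo it. The reporting gap is not established either: sections 9 and 12 place the study under ISO 14155, whose reporting requirements could not be checked here.

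**Conclusion.** No change to the plan follows. The harm needs three things the protocol does not contain: an unplanned look at adequacy results, a reading of benefit as guidance adequacy, and an adequacy proportion used to support a decision. No test, threshold or planned analysis would be altered. If the look did happen, a single one at 10 subjects would inflate a descriptive proportion by 2.2 to 2.6 points and one at 20 by 0.3 to 0.9 points, at assumed true rates of 85 to 95%. Both are well inside sampling error, and exact intervals keep their coverage. A look as early as 5 subjects could add 3.4 to 5.8 points, but the lower exact limit for 5/5 is only 0.025^(1/5) = 48%, so such a result could support little.

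What remains is missing detail. A competent final report will give the number enrolled, why enrolment ended, and an exact interval with any adequacy proportion. Keeping a sponsor's right to close a small feedback study early is a fair trade-off. The judgement would differ if the adequacy proportion were to be compared with a performance goal, because a result-dependent stop could then affect a formal conclusion.

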10. STATISTICAL METHODS

10.1 Statistical Hypothesis

No statistical hypothesis is being tested in this study.

10.2 Sample Size Determination

The sample size is based on the Sponsor's previous clinical experience and the expectation that enough procedures using the OEC Elite will be performed to demonstrate clinical performance.

10.3 Statistical Analysis

No statistical analysis is prospectively planned.

10.3.1 Interim Analysis

No interim analyses are intended to be conducted as part of this study.

10.4 Handling of Missing Data

Analysis will be based on collected data, and no imputation will be done for missing data.

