3. PURPOSE OF THE STUDY

The purpose of the study is to collect survey data on the use of the OEC Elite based on the routine clinical use of the device.

3.1 Study Objectives:

3.1.1 Primary Objective:

The primary objective is to collect investigator feedback on imaging guidance adequacy of the OEC Elite during clinical procedures.

3.1.2 Secondary Objective(s):

The secondary objectives of this study are to collect image data acquired during clinical procedures and to collect investigator feedback via surveys on the use of the system during clinical procedures.

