3.2 Study Endpoints

3.2.1 Primary Endpoints:

The primary endpoint is the per-subject investigator report of imaging guidance adequacy to complete the procedure (Y/N).

3.2.2 Secondary Endpoints:

The secondary endpoints are the total number of surveys reflecting the investigator opinion of procedures performed and the image data collected.

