5.4 Malfunction/Error Handling

The site should report the occurrence and resolution of any procedures terminated due to non-recoverable malfunctions (i.e. malfunctions or errors with OEC Elite that prevent image collection and are not able to be immediately resolved by the device operator). The site should also report recoverable errors (i.e. issues with the device that do not prevent image collection and are able to be resolved immediately by the device operator) and operator errors. The occurrence of any recoverable error, operator error, or non-recoverable malfunction will be reported on the subject's CRF.

In uncommon cases, the research procedures using the investigational device may need to be terminated unexpectedly. If the investigator suspects that a subject would be at increased risk, or that the subject's clinical procedure will not be able to be completed using the investigational device in this study, the investigator may terminate the procedure at any time and for any reason. In some cases, it may not be feasible to end a procedure; in which case, equivalent, site-provided commercial fluoroscopy equipment (such as the predicate device or equivalent) may be used. The site will ensure that access to alternative commercial fluoroscopy equipment is maintained during all procedures. All patient care and management

decisions for terminated procedures will be made outside of this study according to the sites' standard clinical practices and the subject's regular physician's or investigator's medical judgment.

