6. STUDY DATA COLLECTION AND ASSESSMENTS

6.1 Operating Physicians

At the completion of a procedure, the physician (e.g. interventional specialist or surgeon) conducting the procedure will provide feedback on the capability of the system by completing a User Survey. Survey data will be recorded on case report forms (CRFs).

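### Does the lack of a scoring rule for procedures stopped on, or switched from, the OEC Elite bias the primary adequacy result?

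*Combined protocol and SAP*

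**What the plan says.** Section 3.2.1 defines the outcome: "The primary endpoint is the per-subject investigator report of imaging guidance adequacy to complete the procedure (Y/N"). Section 3.1.1 names the device it concerns: "The primary objective is to collect investigator feedback on imaging guidance adequacy of the OEC Elite during clinical procedures".

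The protocol foresees procedures that do not finish on that device. Section 2.5 states: "If imaging is not adequate or diagnostic-quality images cannot be obtained using the investigational device, the subject will not undergo additional investigational imaging". Under section 5.4, "the investigator may terminate the procedure at any time and for any reason", and where stopping is not feasible, "commercial fluoroscopy equipment (such as the predicate device or equivalent) may be used".

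On recording, section 6.1 says of the User Survey: "At the completion of a procedure, the physician (e.g. interventional specialist or surgeon) conducting the procedure will provide feedback". Section 7.3 lists Guidance Adequacy as a CRF entry separate from that survey. Section 5.4 adds: "The occurrence of any recoverable error, operator error, or non-recoverable malfunction will be reported on" the subject's CRF.

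On analysis, section 10.1 tests no hypothesis and section 10.3 plans no statistical analysis. Section 10.4 reads: "Analysis will be based on collected data, and no imputation will be done for missing data".

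**The concern.** The procedures most likely to deserve an N are those that end away from the device. If the survey timing in 6.1 is taken to cover the adequacy item, a terminated procedure might never receive an answer, and under 10.4 an unanswered case leaves the denominator. That missingness would be informative, since the blank is caused by the failure being measured. A switched procedure raises a second question. The endpoint wording does not name the device, so someone might answer Y because the procedure was eventually completed on other equipment.

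At stake is the only primary result. Section 10.2 justifies the sample size by the expectation that enough procedures will be done to show clinical performance, so a summary that reads 100% however many failures occurred would mislead.

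**Working it through.** **Reproducing a planned figure.** There is none to reproduce. Section 4.3 caps enrolment at 40 and lets the sponsor stop earlier. Section 10.2 gives no target rate, precision or power, and 10.3 defines no denominator. What follows is an illustration under assumed failure counts.

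**Formula.** Let n subjects start on the device, d of them fail for device-related reasons, and b of those d be left blank, with every other answer Y. The proportion on collected data is (n − d)/(n − b). With every failure answered N it is (n − d)/n. The difference is b(n − d)/[n(n − b)], which is zero when b = 0 and d/n when b = d.

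**Numbers** (exact Clopper-Pearson 95% intervals):

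| Assumed case | Blanks omitted | Failures answered N | Difference |
|---|---|---|---|
| n=40, d=1, b=1 | 39/39 = 100% (91.0–100) | 39/40 = 97.5% (86.8–99.9) | 2.5 points |
| n=40, d=2, b=1 | 38/39 = 97.4% (86.5–99.9) | 38/40 = 95.0% (83.1–99.4) | 2.4 points |
| n=40, d=2, b=2 | 38/38 = 100% (90.7–100) | 38/40 = 95.0% (83.1–99.4) | 5.0 points |
| n=20, d=1, b=1 | 19/19 = 100% (82.4–100) | 19/20 = 95.0% (75.1–99.9) | 5.0 points |

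In the first row there are 39 Y reports either way. A blank changes the proportion, not the number of Y reports. That number rises only if a switched procedure is answered Y: with d = 2 and both answered Y, the result is 40/40 (91.2–100).

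**How likely is any failure?** The documents give no rate; 2.5 and 5.4 describe such events as unlikely or uncommon. At an assumed 2% or 5% per procedure, the chance of at least one in 40 is 1 − 0.98^40 = 55% or 1 − 0.95^40 = 87%. A failure could well occur. The question is whether following the plan would leave it blank or score it Y.

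**Reading the sections together.**

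1. *Inadequate images.* The trigger in 2.5 is itself a judgement that imaging was not adequate. Set beside 3.2.1 and 3.1.1, the answer for the OEC Elite is N.
2. *Switch to other equipment.* Section 3.1.1 names the OEC Elite, 5.2 has study imaging done with it, and 6.1 asks about the capability of the system. Answering Y because a different system finished the job contradicts all three.
3. *Blank entries.* The timing in 6.1 attaches to the User Survey, while Guidance Adequacy is a separate item in 7.3. Section 11.1.1 has CRFs filled in as information arrives, makes the principal investigator responsible for completion, and provides for corrections at monitoring and data clarification afterwards. Section 4.7 requires a final evaluation on a CRF for withdrawn subjects. A blank on the primary item can be queried.
4. *Visibility.* Section 5.4 puts malfunctions on the CRF, and 8.5 has all device deficiencies collected and investigated. With at most 40 subjects at one site, every such case can be listed.
5. *Malfunction with otherwise adequate images.* Here the text does not settle the answer.

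**The case for a change.** The best case for a change is that the safeguards make failures traceable, but none requires an adequacy answer for a terminated procedure or says what that answer is. Omitting failures can only raise the proportion or leave it unchanged. A descriptive study still needs a numerator and a denominator, and enrolment at consent (4.6) means that enrolled subjects are not automatically the right denominator. Clarifying wording would cost little.

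Part of this stands. The protocol has no explicit rule, and the malfunction case is open. It does not follow that the plan yields a wrong result. Section 10.4 declines to impute; it does not classify a terminated procedure as missing. The bias needs a failure and then either an entry left blank despite the CRF process or a Y that runs against the stated objective.

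A firm scoring rule also has a price. The endpoint is the investigator's own report, and a derived N would override it. Scoring every malfunction N would mix device reliability with image adequacy. Counting unanswered cases as N in a sensitivity analysis would be a form of imputation, which 10.4 rules out. The CRF and any completion guidelines under 11.1.1 are not reproduced, so the absence of an instruction is established only for the protocol text.

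**Conclusion.** No change is called for. This is missing detail that investigators and analysts would fill sensibly: N when the OEC Elite's images were inadequate, a query when the item is blank, and an individual listing of stopped or switched cases. The remaining ambiguity, a malfunction with adequate images, is a fair trade-off between a uniform rule and the investigator's own report.

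The possible overstatement is 2.5 percentage points per blank failure at 40 subjects, or 5 points at an assumed 20, if all failures are blank and all other answers are Y. It is zero if failures are answered N. The failure counts, the blanks and the proportion itself are assumptions; the plan commits to no rate, threshold or test that they could alter. The conclusion rests on reading 3.1.1, 3.2.1 and 7.3 together and on the CRF process in 11.1.1 being followed.
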